### 7.1.3 Treatment period

A treatment cycle is defined as 28 days (4 calendar weeks) for the purposes of scheduling procedures and evaluations. Please refer to [Table 7-1](#) and [Table 7-2](#) for details of the timing of required assessments and [Section 7.1](#) for visit windows.

Participants will be treated until participant experiences unacceptable toxicity, progressive disease and/or treatment is discontinued at the discretion of the investigator or withdrawal of consent/opposition to use data/biological samples as described in [Section 7.1.5](#).

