## 7.2 Assessment types

### 7.2.1 Efficacy assessments

Tumor response will be determined locally according to Response Evaluation Criteria in Solid Tumors (RECIST) 1.1 ([Appendix 1](#)).

Tumor response evaluations will be determined by the local investigators, based on RECIST 1.1. Imaging data will be centrally collected, checked for quality and stored for possible independent review by an imaging CRO designated by Novartis. Independent tumor response evaluations would then be determined according to the Novartis guideline ([Appendix 1](#)), based on RECIST 1.1. For Groups 1 to 4, the results of the central BIRC evaluations may be used for secondary analyses purposes.

CT/MRI scans will be performed at baseline within 28 days (preferably 7 days) before start of treatment and subsequently every 8 weeks from start of Cycle 3 until progression of disease and every 12 weeks from Cycle 13 Day 1 until progression of disease. See [Table 7-3](#) for details. CT/MRI scan will be performed at EOT if not conducted within 30 days prior to EOT. Disease progression follow-up should be performed as described in [Section 7.1.6](#). Depending on regulatory requirements it is allowed to have the EOT scan performed within an extended time frame but not later than 8 weeks from the last CT scan.

For participants in Phase II Group 5 entering the extension treatment period, a new baseline assessment should be performed no more than 28 days before the start of combination therapy. If the scan confirming disease progression on capmatinib monotherapy occurs within 28 days of the first dose of combination therapy, this scan may be used as the baseline scan for combination therapy.

After baseline, all assessments should be performed within  $\pm 7$  days of the scheduled day of assessment. Imaging evaluations subsequent to an off-schedule confirmatory scan should be performed according to the original assessment schedule. The same method of assessment and the same technique should be used to characterize each individual and reported lesion at baseline and during follow up.

If at baseline a participant has a medical contraindication to CT i.v. contrast or develops a contraindication during the trial, a non-contrast CT of chest plus contrast-enhanced MRI of abdomen is acceptable.

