### Phase II part of the study

This is a single arm trial (i.e. no comparator arm) and there is no a priori information as per the FDA Guidance of "situations in which safety concerns may be unusually high" or the participant population being studied are "potentially fragile population such as children, pregnant women or the very elderly, or other vulnerable populations, such as those who are terminally ill or of diminished mental capacity." Thus, an independent data monitoring committee will not be constituted for the Phase II part of this study.

The Novartis clinical team will review the safety data on a regular basis. A review of the safety data and assessment of futility, based on the calculated Bayesian probability of success (PoS) will be performed at the interim analysis of Group 3 (first line) by the Novartis clinical trial team and shared with the investigators in a data review meeting.

At the time of the interim analysis for Group 3, the best overall response for each participant will be derived from the overall lesion response assessments performed by the Investigator. These will be used to calculate the overall response rate for the respective group and a Bayesian analysis will be performed to estimate the PoS of the trial given the current data (see [Section 10.9](#) for details).

It is envisioned that the team may make three types of recommendations at the interim analysis, namely:

- No safety or efficacy issues, ethical to continue the study group as planned
- PoS is too small and the study group is terminated due to lack of significant activity
- Serious safety concerns precluding further treatment in the study group, regardless of efficacy.

At the time of the interim analysis for Group 5, the response for each participant will be derived from the overall lesion response assessments performed by the Investigator. These will be used to calculate the ORR and a Bayesian analysis will be performed to estimate the POS of the trial given the current data (see [Section 10.9](#) for details).

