#### **Best overall response**

BOR is the best response recorded from the start of the treatment until documented radiological disease progression/recurrence. However, any assessments taken more than 28 days after the last dose of study treatment will not be included in the best overall response derivation.

The study requires that for a partial response (PR) or complete response (CR) changes in tumor measurements must be confirmed by repeat assessments performed not less than 4 weeks after the criteria for the response are first met.

BOR will be summarized by treatment group.

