### Group 3 (EGFRmut, T790M negative, any MET, 1L antineoplastic)

One interim analysis for futility will be performed for participants enrolled in Group 3 (participants in first line setting) when approximately 20 participants have completed at least 4 cycles of treatment or discontinued treatment prior that time. A close monitoring of the first 20 measurable participants will be performed. All evaluable participants at the time of the data cut-off for the interim analysis will be used.

The decision whether to continue or stop enrollment and/or treatment will be based on the probability of success (PoS). PoS is the probability to have a positive conclusion at the end of the study, given the interim data. Denoting the number of participants at interim by  $n_1$  and the number of responders at interim by  $r_1$ , PoS is found as

- $PoS = \text{Prob} [\text{at least } x-r_1 \text{ responders in } 40-n_1 \text{ participants} \mid r_1 \text{ responders in } n_1 \text{ participants}]$

The number of responders ( $x-r_1$ ) to be observed in the remaining  $40-n_1$  participants follows a Beta-binomial distribution. This is used in order to calculate PoS.

The enrollment and/or treatment may be stopped at the interim analysis if  $PoS < 0.10$ , i.e., if less than 9 out of the first 20 participants have the best response of CR or PR. The criterion (number of responders) will be based on the actual number of participants in the FAS at the time of the interim analysis.

If futility is concluded, the enrollment of 1L participants (Group 3 and 1L participants in Group 4) may be stopped. The enrollment in opened groups with pre-treated participants will continue.

[Table 10-2](#) provides the probabilities of success at the primary analysis based on different numbers of responders observed at the interim analysis. For 9 or more responders PoS exceeds 0.10 and the study will continue at interim.

**Table 10-2 Probability of success at the primary analysis based on various numbers of responders observed at the IA for Group 3**

Responders at IA out of 20 evaluable participants at IA	Probability of Success
8/20	0.04
9/20	0.14
10/20	0.33
11/20	0.57
12/20	0.79

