### Group 5 (EGFRmut, T790M-, MET GCN $\geq$ 5, 2L, EGFR TKI resistant)

An interim analysis for futility will be performed based on stage 1 of the 2-stage design of Group 5 when 10 participants have completed at least 2 tumor assessments while on treatment with capmatinib monotherapy, had radiological disease progression per RECIST 1.1, or discontinued capmatinib monotherapy treatment prior that time. Recruitment will be on temporary halt while conducting the IA. The IA will be based on the EAS.

The decision to stop for futility at the interim analysis will be based on the predictive probability (PP) that the final observed ORR of capmatinib monotherapy is no worse than the historical control ORR, given the interim observed data (x) and responders among n participants. Based on available data (Soria et al 2015, Mok et al 2017), the ORR in the historical control for this population is expected to be around 35%. Thus, the stop for futility rule is based on

$$PP = \text{Prob}[\text{Final observed ORR of capmatinib monotherapy} \geq 35\% \mid x, n]$$

A minimally informative Beta distribution prior with prior mean equal to 35% will be used, i.e., the prior distribution will be Beta (0.5385, 1) for the futility stopping decision rule calculations at the interim analysis.

The group will be stopped for futility at the interim analysis if the PP <1%, i.e., if 0 response out of the first evaluable 10 participants is observed. For the purpose of the interim analysis a responder is defined as participant having a response of PR or CR per RECIST 1.1.

All evaluable participants at the time of the data cut-off for the interim analysis will be used to obtain the futility boundary using the stopping criteria. The futility boundary will be calculated according to the actual number of evaluable participants (in the EAS) in the interim analysis.

Table 10-3 presents the PP at the final analysis based on different numbers of responders observed at the interim analysis and an observed ORR of not worse than 0.35 for capmatinib monotherapy.

**Table 10-3 Predictive probability (PP) for ORR of capmatinib monotherapy at the final analysis based on various numbers of responders observed at the IA for Group 5**

Responders at IA out of 10 evaluable participants at IA	Predictive probability (PP)
0	0.0000
1	0.0148
2	0.0984
3	0.3207
4	0.6301
5	0.8686
6	0.9720
7	0.9967
8	0.9998
9	1.0000
10	1.0000

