### Group 3 (EGFRmut, T790M negative, any MET, 1L antineoplastic)

The operating characteristics of the statistical design are presented below with the probabilities to stop for futility at the interim analysis and to declare preliminary anti-tumor activity of the study treatment at the primary analysis (observing at least 22 responses in 40 participants) under different true ORR values (see also [Table 10-5](#)).

The actual total sample size in Group 3 may be greater than 40.

- If the true ORR is 40%, it is likely to stop at the interim analysis (probability 0.596) and the probability to declare preliminary anti-tumor activity at the end of the study is low (0.038).
- If the true ORR is 55%, the probability to stop at the interim analysis is low, 0.131, and the probability to declare preliminary anti-tumor activity at the end of the study is 0.553.
- If the true ORR is 70%, it is highly unlikely that the study would be stopped at the interim analysis (probability 0.005) and the probability to declare preliminary anti-tumor activity at the end of the study is very high (0.982).

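### Read with the protocol's own definition of best overall response, the Group 3 futility look counts a response first seen at week 16 as a failure, so the stated 0.131 stopping risk at a 55% ORR is a lower bound.

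*Protocol*

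**What the plan says.** **Trigger and rule.** Section 10.9 (Group 3) places the look "when approximately 20 participants have completed at least 4 cycles of treatment or discontinued treatment prior that time". Enrolment and/or treatment may be stopped if the probability of success (PoS) is below 0.10, which the section translates as "if less than 9 out of the first 20 participants have the best response of CR or PR". PoS takes the interim responder count r1 as fixed and asks whether the other 40 − n1 participants will supply the rest of the 22 responders needed. If futility is concluded, first-line enrolment in Group 4 may stop too.

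**What is counted.** For the Group 3 interim, Section 8.5 says that "the best overall response for each participant will be derived from the overall lesion response assessments performed by the Investigator". Under Best overall response in Section 10.7.2.1, changes in tumour measurements for a PR or CR "must be confirmed by repeat assessments performed not less than 4 weeks after the criteria for the response are first met". Sections 7.2.1 and 14.1.3.1 say the same, and Section 10.5.1 defines the primary endpoint as confirmed response. Section 10.9 (Group 3) does not use the word confirmed. For Group 5 it gives a separate rule: "For the purpose of the interim analysis a responder is defined as participant having a response of PR or CR per RECIST 1.1".

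**Scans.** Section 7.2.1 schedules imaging at baseline and "subsequently every 8 weeks from start of Cycle 3 until progression of disease". Cycles last 28 days (Section 7.1.3).

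**Stated risk.** Section 10.10: "If the true ORR is 55%, the probability to stop at the interim analysis is low, 0.131". Table 10-5 gives a success probability of 0.553 at the same ORR.

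**The concern.** The look and the primary analysis can classify the same participant differently. A PR first seen at week 16 cannot be confirmed before about week 20, so at a cut-off near 16 weeks that participant's best overall response is stable disease. The primary analysis waits for at least 6 cycles (24 weeks), when the response can be confirmed and counted. PoS cannot anticipate this, because only participants outside the first n1 can add responders.

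The boundary is sensitive to this. With 8 confirmed responders and one pending, r1 = 8 gives PoS 0.04 and the boundary is crossed. With r1 = 9, PoS is 0.14 and the group continues (Table 10-2). A single pending scan can decide the matter.

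At stake is a first-line group whose true ORR may equal the 55% that the protocol calls clinically meaningful, together with first-line enrolment in Group 4.

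**Working it through.** **Timeline.** 4 cycles × 28 days = 112 days = 16 weeks. Scheduled scans fall at Cycle 3 Day 1 (week 8), Cycle 5 Day 1 (week 16) and Cycle 7 Day 1 (week 24), each ±7 days. A participant at the minimum has at most the first two. The earliest confirmation of a week-16 response is 16 + 4 = week 20.

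**Reproducing the plan.** Inputs: prior Beta(1, 0.818), stop at 8 or fewer of 20, success at 22 or more of 40.

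- Beta-binomial PoS for 8, 9, 10, 11 and 12 of 20: 0.043, 0.140, 0.326, 0.570, 0.789. Table 10-2 has 0.04, 0.14, 0.33, 0.57, 0.79.
- P(stop) at ORR 55% = P(Bin(20, 0.55) ≤ 8) = 0.1308 (stated 0.131).
- P(success) = P(X1 ≥ 9 and X1 + X2 ≥ 22), with X1 and X2 each Bin(20, 0.55), = 0.5533 (stated 0.553).

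Every row of Table 10-5 reproduces. The table uses one response probability at both looks, so it treats every interim status as final.

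**Allowing for pending responses.** Two assumptions are needed, neither given in the protocol:

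- f: share of eventual confirmed responders still unconfirmed at the cut-off, among participants at minimum follow-up.
- k: how many of the 20 are at minimum follow-up.

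The interim count becomes Bin(20 − k, 0.55) + Bin(k, 0.55 × (1 − f)). P(cross) is the probability that this is 8 or fewer. Pending responders still count towards the final 22 if the group continues. For k = 20 and f = 10%, the interim rate is 0.55 × 0.90 = 0.495 and P(Bin(20, 0.495) ≤ 8) = 0.266.

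Results at true ORR 55%, as P(cross) / P(success):

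| | f = 0 | f = 10% | f = 20% | f = 30% |
|---|---|---|---|---|
| k = 5 | 0.131 / 0.553 | 0.159 / 0.546 | 0.190 / 0.536 | 0.225 / 0.523 |
| k = 10 | 0.131 / 0.553 | 0.191 / 0.535 | 0.265 / 0.506 | 0.352 / 0.464 |
| k = 20 (upper case) | 0.131 / 0.553 | 0.266 / 0.504 | 0.450 / 0.407 | 0.649 / 0.277 |

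P(success) here supposes that crossing the boundary always ends the group, as Table 10-5 does.

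**The case against.** **The interim rule never says confirmed.** Sections 10.5.1 and 10.7.2.1 add that word to the response rate; Section 10.9 (Group 3) does not. If observed PR or CR counts at the look, the problem does not arise. This stands as a limit: the confirmed reading is an inference. It is a reasonable one, because Section 8.5 names best overall response for Group 3, the protocol builds confirmation into that term, and r1 is subtracted from a final count of confirmed responses. Group 5 has its own interim responder sentence and Group 3 has none, although that sentence is also silent on confirmation.

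**Four cycles is a minimum.** With staggered entry, participants enrolled 8 or more weeks before the 20th may already have a week-24 scan, and Section 7.2.1 foresees off-schedule confirmatory scans. A reader might infer that only responses present at week 8 can ever count. The documents do not support that: only participants near minimum follow-up are exposed, and the k = 20 row is an upper case.

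**A pending response is not lost for good.** A reader might infer that it is a permanent failure. It is a failure only inside PoS; if the group continues, it counts at the primary analysis.

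**The rule is non-binding.** Enrolment may be stopped, and the team reviews individual data throughout, so pending responses would be visible. The figures are therefore probabilities of crossing the boundary, not of stopping.

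**Conclusion.** The point holds conditionally. Under the protocol's own definition of best overall response, the Group 3 look leans towards futility, and 0.131 at a 55% ORR is a lower bound. A reader might conclude that 0.131 is miscalculated; it is not. It is exact when all 20 statuses are final.

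The size cannot be fixed from the protocol, which gives neither an accrual rate nor a time-to-response distribution for Group 3. Over f = 10% to 30%, P(cross) runs from 0.159 to 0.225 with 5 participants at minimum follow-up and from 0.191 to 0.352 with 10. The upper case, with all 20, is 0.266 to 0.649. If f is zero, or if unconfirmed responses are counted and all later confirm, it stays at 0.131.

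This is more than a missing detail: applying the definitions as written biases a stopping rule, and one sentence removes the bias.

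**What to change.** State in Section 10.9 that, for the Group 3 interim only, r1 counts confirmed PR or CR plus unconfirmed PR or CR whose confirmation is still pending with no later progression. Keep confirmed ORR for the primary analysis.

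There are two alternatives:

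- Set the data cut-off so that the first 20 have all had the opportunity for a confirmatory assessment of a week-16 response. This delays the look.
- Leave the rule alone and restate the Section 10.10 probabilities as conditional on final interim status, with a range for late responders. This discloses the bias without removing it.

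The cost of the main change is that some pending responses will not confirm, so a weak regimen is stopped less often. Suppose (an assumption) that 5% of participants have a pending PR at the look that later fails to confirm. A regimen with a 40% confirmed ORR then shows 0.40 + 0.05 = 0.45 at the interim, and P(stop) falls from 0.596 to 0.414, the 0.45 row of Table 10-5. The price is mainly extra enrolment rather than false success: with no interim look at all, P(Bin(40, 0.40) ≥ 22) = 0.039, against the stated 0.038.

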### **10.1.1 Full Analysis Set**

The Full Analysis Set (FAS) comprises all participants who have received at least one dose of either capmatinib or nazartinib. Participants will be analyzed according to the planned treatment they have been assigned to. The FAS will be used for all listings of raw data.

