### **10.5.3 Handling of missing values/censoring/discontinuations**

**Incidence of DLTs in Cycle 1:** If a Phase Ib participant is considered as non-evaluable for the DDS, enrollment of a new participant to the current cohort will be considered if there is less than the required number of evaluable participants ([Section 6.2.3](#)).

**Overall response rate:** Participants who have missing BOR will be considered as a treatment failure for the primary analysis of ORR.

Participants who have disease progression and continue to receive study drug after progression will qualify for PD at the time of progression and will be counted as PD in the derivation of efficacy endpoints.

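### The Group 3 futility rule names three conflicting populations, none limited to participants followed long enough to respond; the FAS wording, if applied with enrolment open, tilts the rule towards stopping

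*Protocol*

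**What the plan says.** All of this is in the protocol. Section 10.9 (Group 3) times the look "when approximately 20 participants have completed at least 4 cycles of treatment or discontinued treatment prior that time". The population and the boundary are then described in three ways:

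- "All evaluable participants at the time of the data cut-off for the interim analysis will be used". The header of Table 10-2 also speaks of evaluable participants.
- Stopping corresponds to PoS below 0.10, that is, "if less than 9 out of the first 20 participants have the best response of CR or PR".
- The required responder count is then tied to a third set, everyone in the FAS when the look is taken: "The criterion (number of responders) will be based on the actual number of participants in the FAS at the time of the interim analysis".

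Section 10.1.1 says that the FAS "comprises all participants who have received at least one dose of either capmatinib or nazartinib", with no minimum follow-up. For Groups 1 to 4, the available text defines evaluable for efficacy only in Section 10.1.3, for the per-protocol set, as one usable post-baseline response. Section 10.5.3 states: "Participants who have missing BOR will be considered as a treatment failure for the primary analysis of ORR".

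The rule is permissive: "The enrollment and/or treatment may be stopped at the interim analysis if" PoS is too low. A futility conclusion may also close first-line enrolment in Group 4. For Group 5 the same section states a recruitment halt during the interim analysis. No halt is stated for Group 3.

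**The concern.** The trigger fixes when the look takes place. It does not fix who is counted. A cycle is 28 days (Section 7.1.3), so 4 cycles are 16 weeks. The first post-baseline scan is at the start of Cycle 3, after 8 weeks (Section 7.2.1), and a response must be confirmed at least 4 weeks later. A participant first dosed less than 8 weeks before the cut-off therefore has no scheduled scan on which to respond. One dosed less than about 12 weeks before, or 16 weeks on the regular scan schedule, cannot have a confirmed response. Both are in the FAS.

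If such participants are counted, they raise n1 in the PoS formula and cannot raise r1. The observed rate is diluted and the required number of responders goes up. At stake is a decision on all first-line enrolment, taken on a PoS that no longer means what Table 10-2 says it means.

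**Working it through.** **Inputs.** Prior Beta(1, 0.818) and success at 22 or more of 40 (Section 10.5.2.2); PoS limit 0.10 and the beta-binomial method (Section 10.9); stated operating characteristics (Section 10.10, Table 10-5). The number m of participants dosed too recently to respond is an assumption.

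**Formula.** With r1 responders among n1 participants, PoS = P(Y ≥ 22 − r1), where Y ~ Beta-binomial(40 − n1; 1 + r1, 0.818 + n1 − r1). The boundary is the smallest r1 with PoS ≥ 0.10.

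**The plan's own figures first, n1 = 20.**

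- Final rule: 22/40 gives a posterior median of 0.551 and P(ORR < 40%) = 0.025, so both conditions are met. 21/40 gives 0.527 and 0.050, so the median condition fails.
- r1 = 8: Y ~ Beta-binomial(20; 9, 12.818), P(Y ≥ 14) = 0.043.
- r1 = 9: Y ~ Beta-binomial(20; 10, 11.818), P(Y ≥ 13) = 0.140.
- r1 = 10, 11, 12: 0.326, 0.570, 0.789.

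These agree with Table 10-2. The boundary is 9, and P(Bin(20, p) ≤ 8) is 0.596, 0.131 and 0.005 at p = 0.40, 0.55 and 0.70, as in Table 10-5. The stated success probabilities (0.038, 0.553, 0.982) also reproduce. All of this treats the 20 as having had full opportunity to respond.

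**FAS wording with m extra participants, none yet responding.** Now n1 = 20 + m, and responders come only from the 20 mature participants. The probability of crossing the boundary is P(Bin(20, p) ≤ boundary − 1).

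| m | n1 | Boundary | ORR 55% | ORR 70% |
|---|---|---|---|---|
| 0 | 20 | 9 | 0.131 | 0.005 |
| 2 | 22 | 10 | 0.249 | 0.017 |
| 5 | 25 | 12 | 0.586 | 0.113 |
| 10 | 30 | 15 | 0.945 | 0.584 |

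An example with m = 5: 11 responders among 20 mature participants give PoS 0.570. Counted as 11/25, Y ~ Beta-binomial(15; 12, 14.818) and P(Y ≥ 11) = 0.057, which is below 0.10. The responders are the same and the decision is reversed.

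**Some responses already visible.** If the m participants already show a share of their eventual responses:

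| m | Share visible | ORR 55% | ORR 70% |
|---|---|---|---|
| 5 | 25% | 0.468 | 0.066 |
| 5 | 50% | 0.360 | 0.035 |
| 10 | 25% | 0.805 | 0.296 |
| 10 | 50% | 0.613 | 0.119 |

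**Does the evaluable wording avoid this?** In part. It drops participants without a scan. On the Section 10.1.3 definition it still admits someone with one scan at week 8 and no opportunity for confirmation.

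**The case against.** A reader might infer that the protocol settles on the whole FAS as denominator, that newly dosed participants are by rule non-responders, and that an effective regimen will therefore be stopped. The text does not support this.

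- The FAS sentence is one of three wordings. It can be read as saying only that the cut-off is recalculated because the trigger is approximately 20. The parallel Group 5 sentence refers to evaluable participants.
- Continued enrolment is inferred from the absence of a stated halt. The design description in Section 4.1 was not available here.
- The missing-response rule in Section 10.5.3 is written for the primary analysis. Section 8.5 derives the interim response from lesion assessments, and a participant with none has nothing to derive from.
- Participants dosed 8 to 16 weeks before the cut-off may already show a response, and the interim criterion does not itself say confirmed. Rows with no response among the m participants are the worst case.
- Stopping is discretionary, and the results go to a data review meeting with the investigators.
- The SAP, not shown, may define the interim set.

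All of this limits the claim. It does not remove the conflict. The protocol itself ties the criterion to the FAS, so this is stated text and not a detail left open. Discretion does not correct a PoS calculated on the wrong n1, and the three wordings can lead to opposite decisions on the same data.

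**Conclusion.** The point holds as a contradiction in the interim population with a conditional consequence. The Group 3 boundary and its operating characteristics are correct for 20 mature participants, and no sentence in Section 10.9 restricts the count to such participants. Under the FAS wording with enrolment open, the error is towards stopping.

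Its size cannot be fixed from the protocol, which gives no accrual rate in the part available. It is modest for an active regimen when few recently dosed participants are counted (0.017 at ORR 70% with two) and serious when there are many (0.584 with ten and none yet responding, 0.119 if half of their eventual responses are visible). These are probabilities of crossing a non-binding boundary, not of the group actually being stopped.

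A reader might extend the point to the Group 5 interim. That is not supported here: its section states a recruitment halt during the analysis, and no calculation was made for it.

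**What to change.** In Section 10.9 (Group 3), replace the sentences on evaluable participants and on the FAS by one definition, for example: *The interim analysis includes only FAS participants who, at the data cut-off, have completed at least 4 cycles or stopped treatment earlier; n1 and r1 are counted in this set, and the boundary is recalculated as PoS < 0.10 for this n1.* Present 9/20 and Table 10-2 as the case n1 = 20, and use the same term in the table header.

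With n1 = 20 mature participants responding at the true ORR, this returns exactly the stated design: stopping probabilities 0.596 / 0.131 / 0.005 and success probabilities 0.038 / 0.553 / 0.982 at ORR 40 / 55 / 70%. Taking participants consecutively by date of first dose would also keep recent early discontinuations from entering ahead of contemporaries still on treatment.

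The cost is one sentence in the protocol, repeated in the SAP. It needs no extra participants, data or visits.
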